12.4 Proposed Statistical Analysis

A CONSORT diagram depicting the flow of participants through the study will be reported. Descriptive statistics will be used to report baseline characteristics by treatment group and overall: continuous variables will be summarised by the mean, standard deviation, median minimum and maximum; categorical variables will be summarised using the number and percentage in each category. Log transformation will be used where appropriate.

We will keep missing data to an absolute minimum, but where there is missing data those records will be removed from the analysis; if missing data rates are substantial the effect of this will be investigated using sensitivity analyses.

Binary outcomes (including the primary outcome) will be reported by treatment group and overall using the proportion and exact 95% confidence interval. Binary outcomes will be compared within dosing cohort between the PP100-01+NAC and the NAC alone patients using a difference in proportions and its exact 95% confidence interval. Binary outcomes will be compared between each of PP100-01 dosing groups A, B and C and the combined NAC alone group in the same way.

Continuous outcomes will be reported by treatment group and overall using the mean and 95% confidence interval. Continuous outcomes will be compared within dosing cohort between the PP100-01+NAC and the NAC alone patients using the difference in means and its 95% confidence interval. Continuous outcomes will be compared between each of PP100-01 dose groups A, B and C and the combined NAC alone group in the same way. The continuous outcome analyses listed above will be repeated using the change from baseline in each continuous outcome.

3. Overall Statistical Principles

3.1 SAP objectives

The objective of this SAP is to describe the statistical analyses contributing to the final report and publication(s) of the POP trial. Analyses of the experimental biomarkers such as CK18, microRNA MiR122, GLDH, mitochondrial DNA are not included and will be covered in a separate analysis plan.

3.2 General principles

In general terms, categorical data will be presented using counts and percentages, whilst continuous variables will be presented using the mean, standard deviation (SD), median, minimum, maximum and number of patients with an observation (n), using a format similar to example tables 1 and 2 below. Data will be summarised overall and split by PP100-01 treatment group (NAC alone; NAC + 2µmol/kg PP100-01; NAC + 5µmol/kg PP100-01; NAC + 10µmol/kg PP100-01) and timepoint, where applicable.

Example 1. Data presentation for categorical data

Variable	Timepoint	Category	NAC alone	NAC + 2µmol/kg PP100-01	NAC + 5µmol/kg PP100-01	NAC + 10µmol/kg PP100-01	Overall
			N=xx	N=xx	N=xx	N=xx	N=xx
Variable A	Timepoint x	Category 1	xx (%)	xx (%)	xx (%)	xx (%)	xx (%)
	
		Category n	xx (%)	xx (%)	xx (%)	xx (%)	xx (%)

Example 2. Data presentation for continuous data

Variable	Timepoint / visit	Statistic	NAC alone	NAC + 2µmol/kg PP100-01	NAC + 5µmol/kg PP100-01	NAC + 10µmol/kg PP100-01	Overall
			N=xx	N=xx	N=xx	N=xx	N=xx
Variable A	Timepoint x	Mean (SD)	Xx	xx	xx	Xx	xx
		Median	Xx	xx	xx	Xx	xx
		Min, Max	xx, xx	xx, xx	xx, xx	xx, xx	xx, xx
		n	Xx	xx	xx	Xx	xx

Two-sided 95% confidence intervals (CIs) will be presented.

Where there are missing data for an outcome variable, in the first instance, a complete case analysis will be performed for that outcome, unless otherwise specified. In tabulations, numbers of missing observations will be provided, but percentages will not include them.

Normality will be examined by normal probability plots. If the distributional assumptions for the parametric approach are not satisfied, further data transformation (to alleviate substantial skewness or to stabilise the variance), or other suitable methods will be considered. This will be documented in the statistical results report together with the reasoning supporting the action taken, if applicable.

All analyses and data manipulations will be carried out using SAS [1].

3.3 Analysis Populations

The analysis populations defined for the statistical reporting of the trial are as follows:

Full analysis population (FA) Patients will be included in the full analysis population, the primary population for analysis of efficacy, if they have received any PP100-

01 or NAC. Data will be analysed according to the randomised treatment group.

Per protocol population (PP) The stringent per protocol population includes patients from the full analysis population for whom the study protocol has been followed without any major violations.

Safety population The population for safety analysis will be patients who have received any PP100-01 or NAC. Data will be analysed according to the treatment received (NAC plus PP100-01; or NAC alone). Any patient who withdraws during the treatment phase of the study will be included in the safety population.

4. List of Analyses

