Anaphylactoid reactions, characterised by symptoms such as rash, wheeze, and hypotension are thought to be dose and rate-related. Studies in Edinburgh have demonstrated that these are mediated by histamine release (Pakravan et al 2008). In one prospective randomised controlled study, the rate of anaphylactoid reactions was 18% (Kerr et al 2005). A recent prospective study of patients treated with the standard intravenous NAC regimen in the Edinburgh toxicology unit showed that around 15% developed anaphylactoid reactions (Pakravan 2008) and similar figures have been reported from Newcastle (Fathalla et al 2008). Anaphylactoid reactions are managed by interrupting the infusion temporarily and administering an antihistamine and bronchodilators. Most affected patients can be restarted on NAC at a lower infusion rate. Females, asthmatics and patients with low plasma APAP concentrations are at higher risk of anaphylactoid reactions (Schmidt et al 2001, Waring et al 2006, Pakravan 2008) and fatal adverse reactions have been reported, although these are rare.

Although highly effective, especially if started within a few hours of paracetamol overdose, the current licensed intravenous 20.25hr NAC regimen has several disadvantages. Firstly, intravenous NAC is commonly associated with adverse effects, the most common being nausea, vomiting and anaphylactoid reactions. Anaphylactoid reactions appear related to the rate of infusion of NAC and its concentration in blood. Thus they are most common during, or soon after, the initial high dose infusion. Secondly, the infusion schedule is complex, requiring prescription of three different infusions, and this contributes to a high risk of medication errors, which may have serious, potentially life-threatening, adverse outcomes. Thirdly, the required duration of the infusion regimen results in prolonged hospital stay, especially as patients with paracetamol overdose often present during the night (Thanacoody et al 2013).

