4.4 Primary Outcome (Safety population)

The number and percentage of patients experiencing an adverse event (AE) will be summarised by treatment group and overall. Further tabulations in the same format will be reported for subsets of AEs according to the following criteria:

- Serious adverse events (SAEs)
- AEs starting after the commencement of NAC treatment and within 7 days of consent
- SAEs starting after the commencement of NAC treatment and within 7 days of consent
- Intensity (mild/moderate/severe)
- Treatment given in response to AE (yes/no)

- Outcome (recovered/improved/unchanged/deterioration/death)
- Relationship to NAC (unrelated/possibly related/probably related/definitely related)
- Relationship to PP100-01 (unrelated/possibly related/probably related/definitely related)
- Action taken with NAC (none/interrupted/stopped entirely)
- Action taken with PP100-01 (none/interrupted/stopped entirely)¹
- Unexpected with, and related to, NAC
- Unexpected with, and related to, PP100-01
- Suspected unexpected serious adverse reaction (SUSAR), subcategorised into SUSAR to NAC; SUSAR to PP100-01; SUSAR to NAC and PP100-01

The number and percentage of patients experiencing an adverse event will also be reported according to MedDRA system organ class (SOC). Results will be presented separately for AEs not classified as serious, for SAEs and for all AEs. Events will be summarised by (a) treatment group and overall, and (b) by treatment received (NAC or PP100-01+NAC) within each dosing cohort.

Primary analysis

The numbers of participants experiencing AEs and SAEs will be reported by treatment group and overall using the proportion and exact 95% confidence interval. AE and SAE proportions will be compared within each dosing cohort between the PP100-01+NAC and the NAC alone patients using a difference in proportions and its exact 95% confidence interval. AE and SAE rates will be compared between each of the PP100-01 2µmol/kg, 5µmol/kg and 10µmol/kg groups and the combined NAC alone group in the same way.

If the limited sample size or a small number of observed events leads to a lack of interpretability of the formal analysis confidence intervals, the analysis of the primary outcome will be restricted to descriptive summaries only.

Missing data

We do not anticipate missing data impacting on the analysis of the routinely recorded adverse event data that form the primary outcome.

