4.9 Data listings

Consented patients

Data will be listed for those patients who, after having consented to participate, underwent baseline examinations required for inclusion into the study but who, because a criterion for exclusion was met or for other reasons, were not included in the study. Patient ID and reason(s) for exclusion will be listed.

Withdrawals

Patient ID and all reasons for withdrawal will be listed for patients who have withdrawn from the study.

Medical History (FA)

Medical history will be presented in a line listing, ordered by treatment group and patient ID, of the descriptive text of each event/condition and whether it was classified as past medical history or a presenting complaint.

Adherence with allocated treatment (FA)

Data listings will be provided, ordered by treatment group and patient ID, of the reasons for:

- Temporary stopping of NAC treatment
- Permanent stopping of NAC treatment
- PP100-01 not being given or PP100-01 being stopped early

Protocol deviations and violations (FA)

A listing of protocol deviations and violations will be provided, ordered by treatment group, patient ID and study time point.

Primary outcome (Safety)

Details of adverse events will be listed, ordered by treatment group, patient ID and start date. The listing will include:

- Event category (as recorded on CRF)
- Start date and time
- Date and time resolved
- Seriousness (yes/no)
- SUSAR (yes/no)
- Intensity (mild/moderate/severe)
- Treatment given in response to AE (yes/no)
- Outcome (recovered/improved/unchanged/deterioration/death)
- Relationship to NAC (unrelated/possibly related/probably related/definitely related)
- Relationship to PP100-01 (unrelated/possibly related/probably related/definitely related)
- Action taken with NAC (none/interrupted/stopped entirely)
- Action taken with PP100-01 (none/interrupted/stopped entirely)
- Expectedness with NAC (expected/unexpected/NA)
- Expectedness with PP100-01 (expected/unexpected/NA)

Concomitant Medication (FA)

Three concomitant medication data listings will be provided, one for medications in the 30 days preceding randomisation; the second for medications recorded as “ongoing” at baseline; and a third for those started on or after the date of consent. Each listing will be ordered by treatment group, patient ID and start date, and will contain: Patient ID; Randomisation date; Category; Medication; Start date; Stop date; Ongoing; Dose & Units; Frequency; Route.

5. Derived variables

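### In the primary safety comparison, a patient allocated to PP100-01 but never given it is counted as NAC alone, and one such patient can noticeably move an estimate whose comparator is 2 or 6 patients

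*SAP*

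**What the plan says.** - **Who is in the safety population (SAP 3.3, repeating Protocol 12.2).** "The population for safety analysis will be patients who have received any PP100-01 or NAC". Patients are then grouped as treated, with only two categories: "Data will be analysed according to the treatment received (NAC plus PP100-01; or NAC alone".
- **Where it is used.** SAP 4.4 applies this population to the primary outcome. Within cohorts, "AE and SAE proportions will be compared within each dosing cohort between the PP100-01+NAC and the NAC alone patients". Each dose is also compared with all NAC-alone patients together: "10µmol/kg groups and the combined NAC alone group in the same way". SAP 4.6 analyses anaphylactoid reactions in the same population by the same method.
- **Order of events.** Randomisation is at study entry (Protocol 6.6.1; under Screening in the table in 7.2). PP100-01 is given at about 2 h, after the NAC loading dose (Protocol 7.1.7).
- **AE window.** AEs are recorded from consent (Protocol 10.3). The only onset-time subset in SAP 4.4 starts when NAC starts, so it still includes loading-phase events.
- **Undosed patients are foreseen.** SAP 4.3 has categories for NAC stopped for good in the first infusion and for a bolus that was not started. SAP 4.9 lists reasons for "PP100-01 not being given or PP100-01 being stopped early".

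**The concern.** As-treated grouping is usual for safety data. It is awkward here because the control treatment is also the first 2 h of the experimental treatment. A patient allocated to PP100-01 who leaves or is stopped before the bolus has received exactly what the plan calls NAC alone, and the two-category rule sends the patient there. The reason for not being dosed may itself be an early AE, so the move need not be random with respect to the outcome.

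The comparators are so small that one extra patient changes the estimate visibly, and this is the primary outcome. No AE analysis by randomised group is planned, nor one restricted to events after the PP100-01 time point, so no planned table corrects the shift. If the formal intervals prove uninterpretable, SAP 4.4 falls back to descriptive summaries, which use the same grouping.

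**Working it through.** **Plan's own figure.** 3 cohorts x (6 + 2) = 24 patients, as stated. The planned comparisons are therefore 6 v 2 within cohort and 6 v 3 x 2 = 6 against combined NAC alone.

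**Effect on the comparator.** Let the randomised NAC-alone group have x patients with an AE out of n. One undosed PP100-01 patient moves in:

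- with an AE: (x+1)/(n+1) - x/n = (n-x)/(n(n+1)), which raises the comparator;
- without an AE: x/(n+1) - x/n = -x/(n(n+1)), which lowers it, or leaves it unchanged if x = 0.

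**Benchmark.** The moved patient's event precedes any PP100-01, so it cannot be PP100-01 harm. The like-for-like contrast is therefore events from 2 h onward in patients who reached 2 h.

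**Illustration (assumed counts).** As randomised, 4/6 on PP100-01 have an AE, against 1/2 within cohort or 3/6 combined. One PP100-01 patient is undosed. Every other AE starts after 2 h, and all NAC-alone patients reach 2 h.

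| Undosed patient | Comparison | From 2 h onward | As treated |
|---|---|---|---|
| Had an AE | Within cohort | 3/5 - 1/2 = +10 | 3/5 - 2/3 = -7 |
| Had an AE | Combined | 3/5 - 3/6 = +10 | 3/5 - 4/7 = +3 |
| No AE | Within cohort | 4/5 - 1/2 = +30 | 4/5 - 1/3 = +47 |
| No AE | Combined | 4/5 - 3/6 = +30 | 4/5 - 3/7 = +37 |

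The PP100-01 proportion is the same in both columns, so the whole gap comes from the comparator. It is 1/6 = 17 points for n = 2, x = 1, and 3/42 = 7 points for n = 6, x = 3. The sign depends on whether the moved patient had an AE.

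**Less common events.** With x = 0 and one moved event, the comparator rises by 2/6 = 33 points (n = 2) or 6/42 = 14 points (n = 6). With one event among the five dosed patients (exact unconditional 95% CIs):

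- Within cohort: 1/5 v 0/2 = +20 (-65 to +84) from 2 h onward; 1/5 v 1/3 = -13 (-76 to +54) as treated.
- Combined: 1/5 v 0/6 = +20 (-39 to +72) from 2 h onward; 1/5 v 1/7 = +6 (-48 to +59) as treated.

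**Very common events.** With x = n the shift is zero: 6/6 v 2/2 as randomised becomes 5/5 v 3/3 as treated, a difference of 0 both ways.

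**How likely is it?** The case that favours PP100-01 needs a patient who has a pre-dose AE and is then not dosed. The documents give no such rate. If r is the pre-dose reaction rate and f the share of reactors never dosed, the chance of at least one such patient among 18 is 1 - (1 - rf)^18. Both inputs are assumptions:

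- r = 5%, f = 25%: rf = 1.25%, chance 20%.
- r = 15%, f = 100%: rf = 15%, chance 95%. This extreme takes the rate of about 15% that Protocol 2.2.2 reports for the 20.25 h regimen and supposes that no reactor is ever dosed.

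A smaller f would put the chance below 20%.

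**The case against.** The strongest reply is that this is conventional grouping, fixed by Protocol 12.2, with little consequence in a 24-patient exploratory trial whose intervals exclude almost nothing. Each case would also be visible. SAP 4.3 counts boluses not started, SAP 4.9 lists the reasons and gives every AE with its start time and its relationship to each drug, and SAP 4.4 tabulates AEs by relationship to PP100-01. The safety committee reviews each cohort. All of this is fair, and it keeps the point modest. What it leaves standing is that the listings disclose the shift but no planned comparison removes it.

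A reader might infer more than the documents support:

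- **That the rule always favours PP100-01.** It does so only if the moved patient had an AE. Patients who leave for other reasons can push the other way, and exclusion criterion 9 already screens out likely self-dischargers.
- **That early reactions make it near-certain.** Protocol 2.2.2 says of anaphylactoid reactions: "Thus they are most common during, or soon after, the initial high dose infusion". That sentence concerns the 20.25 h regimen. Sections 2.2.2 and 3.2 report fewer reactions with the 12 h regimen used here, and section 9.3 manages reactions by pausing and restarting. If 5-15% of patients were undosed for any reason (an assumption), the chance of at least one among 18 would be 60-95%, but that counts patients without an AE too.
- **That a harm signal of +17 points (4/6 v 3/6) is lost.** That figure charges a NAC-only event to PP100-01; the fair starting point in the illustration is +10.

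Replacement (Protocol 6.7) could restore six dosed patients, so 3/5 may not be the final PP100-01 count. It would not take the moved patient out of the comparator.

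**Conclusion.** The mechanism follows from the wording of SAP 3.3 and 4.4 and from the order of randomisation, loading dose and bolus. One undosed patient with a pre-dose AE moves the illustrated difference from +10 to -7 points within cohort and from +10 to +3 against combined NAC alone. One without an AE moves it from +30 to +47 and from +30 to +37.

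These sizes rest on assumed event counts, on all other AEs starting after 2 h, and on exactly one moved patient. How often this would happen is not known from the documents and may be small. The documents do not support saying that the rule would hide or reverse an established harm signal: the intervals calculated above span zero under either grouping, and against combined NAC alone the single move in these examples attenuates rather than reverses. For the proportion with any AE, the effect disappears if nearly everyone has one. It matters mainly for SAEs, anaphylactoid reactions and other less common events. This is a cheap improvement, and the as-treated analysis need not be replaced.

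**What to change.** Keep the as-treated table that Protocol 12.2 requires, and in SAP 3.3, 4.4 and 4.6:

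1. Show patients allocated to PP100-01 but never given it in a separate row, rather than pooling them with patients randomised to NAC alone.
2. Add comparisons of AEs, SAEs and anaphylactoid reactions restricted to events starting from the 2 h time point, among patients in both arms who reached it. Define reaching that point identically in both arms, so that the restriction does not itself unbalance them.
3. Place an as-randomised AE/SAE table alongside.

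No new data are needed, because AE start times are already collected for the listing. The cost is SAP wording, one or two extra tables and slightly smaller denominators in the added comparison. Loading-phase events remain in the as-treated table and the listings.

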4.1 Recruitment and retention

The date of first and last patient randomised, and the numbers of patients identified, eligible and randomised, will be reported.

A CONSORT flow diagram will be provided by the POP Trial Manager.

This will present the number (%) of patients, split by treatment group, as follows:

- Randomised
- Receiving at least one dose of study medication
- Completing the trial
- Discontinuing from the trial

In addition, reasons for non-inclusion in the study (prior to randomisation) will be categorised.

The number of patients discontinued early from the study will be summarised by reason for withdrawal and by treatment group.

4.2 Baseline characteristics (FA)

The baseline patient characteristics listed in this section (recorded at either Screening, Timepoint 0 or Baseline [Pre PP100-01]) will be summarised by randomised treatment and overall for the FA population.

- Participant details
 - Age (years)
 - Height (cm)
 - Weight (kg)
 - Body Mass Index (kg/m²)
 - Ethnicity
 - Gender (male/female)

- Childbearing potential (yes/no) [Female participants only]
- Overdose details
 - Time from paracetamol ingestion to presentation at hospital (hrs)
 - Type of overdose (acute within 8hrs of NAC starting / acute more than 8hrs before NAC starting / staggered intentional / supratherapeutic / not known)
 - Amount of paracetamol ingested known (yes/no)
 - Total paracetamol ingested (g)
 - Other drugs ingested
 - Anticoagulants
 - Non-opioid analgesics
 - NSAIDs
 - Cardiovascular drugs
 - Alcohol
 - Opioids
 - SSRIs
 - Tricyclic antidepressants
 - Benzodiazepines
 - Other
- Concomitant medications during preceding 30 days (tabulated by category and whether ongoing)
- Physical examination (each classified as Normal / Abnormal not Clinically Significant / Abnormal Clinically Significant)
 - Cardiovascular
 - Respiratory
 - Gastrointestinal
- Vital signs
 - Systolic blood pressure (mmHg)
 - Diastolic blood pressure (mmHg)
 - Pulse (bpm)
 - Respiratory rate (per minute)
 - Temperature (°C)
 - Oxygen saturation (%)
- ECG (Normal / Abnormal not Clinically Significant / Abnormal Clinically Significant)
- Clinical bloods
 - Paracetamol level (mg/L)
 - INR
 - PT (sec)
 - ALT (U/L)
 - Alkaline phosphatase (U/L)
 - Bilirubin (µmol/L)
 - Creatinine (µmol/L)
 - Haemoglobin (g/L)
 - Urea (mmol/L)
 - MCV (fL)

- WBC ($\times 10^9/L$)
- Sodium (mmol/L)
- Potassium (mmol/L)

No formal statistical testing of baseline characteristics will be performed.

4.3 Adherence with allocated treatment (FA)

No formal statistical testing will be performed. The following will be summarised by treatment group and overall:

- Numbers of patients who were randomised but never treated with either NAC or PP100-01.
- NAC treatment
 - Time from ingestion of paracetamol to start of NAC treatment (hrs)
 - 12 hour NAC regimen
 - Completed without stopping
 - Completed with stop(s) and restart(s)
 - Stopped permanently during first infusion
 - Stopped permanently during second infusion
 - Not started
 - Percentage of intended dose received
(see Appendix 1 for weight-based lookup table for intended dose)
 - Number of additional NAC infusions after 12 hour regimen
(none / 1 / 2 / more than 2)
- PP100-01 treatment
 - Time from ingestion of paracetamol to start of PP100-01 treatment (hrs)
 - Bolus status
 - Completed
 - Stopped early
 - Not started
 - Percentage of intended dose received
 - PP100-01 level at 2, 10 and 20hrs

